## 3.1.2 Laboratory Measurements

**MELD-Na score**. MELD-Na score is calculated using a patient's laboratory values for serum bilirubin, serum creatinine, serum sodium, and the international normalized ratio for prothrombin time (INR). This version of the MELD calculation (MELD-Na) is the United Network for Organ Sharing (UNOS) 2016 modification of the original model to include serum sodium as a factor. The score is calculated as:

MELD-Na = 1.32 x (137 - sodium [mEq/L]) - [0.033 x MELD x (137 - sodium [mEq/L])]

If the patient has undergone dialysis at least twice within the last seven days, then the factor used for serum creatinine should be 4.0. Any value less than one is given a value of 1 (i.e., if bilirubin is 0.8 a value of 1.0 is used) to prevent the occurrence of scores below 0 (because any positive value below 1 the natural logarithm would yield a negative result). The upper limit of serum creatinine is capped at 4.0. The lower limit of serum sodium (Na) is capped at 125, and the upper limit is capped at 137.

MELD-Na score may be computed using the following online calculator: https://optn.transplant.hrsa.gov/resources/allocation-calculators/meld-calculator/

Physiological Model for End-Stage Liver Disease (MELD) must be less than 30 at the time of screening. After enrollment, if a patient's MELD increases to 30 or greater, they can still be eligible.

**Research blood specimen.** A blood specimen of approximately 20 mL will be collected from each participant for research purposes for measurement of protocol-specific biomarkers and biobanking. See *Laboratory Manual* for research blood collection and processing details.

**Eligibility blood specimen.** A blood specimen of approximately 15 mL will be collected from each participant at the Screening eligibility visit to confirm eligibility, including AFP, a blood chemistry and prothrombin time (PT/INR). If a patient's lab results are current (within the past 30 days) in the medical record and within eligibility range, labs will not be re-tested at the Screening visit. See section 6.5 for lab details.

**Clinical blood specimen**. A blood specimen of approximately 10-15 mL will be collected from each participant for blood tests to establish baseline levels and monitor for potential adverse effects of the intervention. Clinical labs include blood chemistry, lipid panel, hemoglobin A1C, creatine phosphokinase (CPK), and prothrombin time. If a patient's lab

results are current (within the past 30 days) in the medical record, labs will not be retested. See section 6.5 for clinical lab details.

**Pregnancy test.** Women who are able to become pregnant must have a confirmed negative pregnancy test result prior to enrollment. Women ≥ 50 years of age who have not had a menstrual period in the past year; and women who have had a hysterectomy, both ovaries removed, or a tubal ligation, will not be required to have a pregnancy test. Should a woman become pregnant or suspect she is pregnant while participating in this study, she should inform her study physician immediately. Women who are able to become pregnant must agree to use adequate contraception (hormonal or barrier method of birth control; abstinence) prior to study entry and for the duration of study participation. Should a woman become pregnant or suspect she is pregnant while participating in this study, she should inform her study physician immediately.

**Liver stiffness.** MRE will be utilized to measure liver stiffness. If the subject has a contraindication to MRE, a FibroScan can be used instead. Subject must use the same modality of either MRE or FibroScan throughout their participation in the study in order to assess intra-individual change using the same procedure.

Liver fat fraction. MRI-PDFF will be utilized to measure fat fraction.

**Transplant tissue specimen.** For all patients who enter the trial and receive a liver transplant before the end of this study, we will collect explant tissue (from the native liver), that would otherwise be discarded, to examine biomarkers in liver tissue that are putatively related to HCC risk, progression, or statin intervention. See *Laboratory Manual* for tissue collection and processing details.

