#### Study Visit 2 (30 days ± 5 days after initiation of intervention)

[figure not shown]
Review medical history, medications, and laboratory test results; symptom assessment; ECOG performance status; blood draw; collect study drug and diary; assess compliance (pill count); review study diary; assess adverse events; review inclusion/exclusion criteria; dispense study drug and diary

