## 1.2 Study Agent

[figure not shown]

Figure 1. Molecular structure of pravastatin

Pravastatin (see Figure 1) is a lipid-lowering agent pravastatin is a derivative of ML236B (compactin), which was identified in a fungus called Penicillium citrinum in the 1970s. It is an inhibitor of 3-hydroxy-3-methylglutaryl-coenzyme A (HMG-CoA) reductase. This enzyme catalyzes the conversion of HMG-CoA to mevalonate, an early and rate-limiting step in the biosynthesis of cholesterol. The empirical formula of pravastatin is C23H36O7 and its molecular weight is 424.534 g/mol. Pravastatin sodium tablets, USP are available for oral administration as 10 mg, 20 mg, 40 mg, and 80 mg tablets. Inactive ingredients include: croscarmellose sodium. lactose

monohydrate, magnesium oxide, magnesium stearate, microcrystalline cellulose and povidone. The 10 mg tablet also contains ferric oxide red, the

20 mg and 80 mg tablets also contain ferric oxide yellow, and the 40 mg tablet also contains D & C yellow No. 10 aluminum lake & FD & C blue No. I aluminum lake.

Pravastatin a commonly prescribed HMG-CoA reductase inhibitor, which has a widely accepted tolerability profile with few serious side effects (21-23). Potential, but uncommon side effects include muscle, liver, and kidney problems. Elevated levels of creatine kinase and rhabdomyolysis occur in <1% of consumers, and myalgia, or muscle ache or weakness, can occur in approximately 5% of consumers (21-23). Historically, there has been reluctance to prescribe statins to patients with preexisting liver disease due to concerns regarding additional liver injury and diabetes (24). However, in recent years, the benefits of statin use have proven to substantially outweigh the minimal potential for adverse events in patients with liver disease: statins delay liver disease progression, improve survival, reverse non-alcoholic steatohepatitis, and ameliorate metabolic syndrome (25-28).

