#### 5.3 Blinding/Unblinding

Due to the objectives of the study, the identity of test and control treatments will not be known to investigators, research staff, or subjects. The following study procedures will be in place to ensure double-blind administration of study treatments.

- The study biostatisticians will set up randomization blocks.
- After registration, participants will be randomized to treatment with the study agent or placebo
- Investigators and participants will be blinded as to the result of randomization. The following people will be unblinded: the study biostatisticians at Cedars-Sinai and the investigational pharmacists at each participating site.
- The investigational pharmacist will manage the study agent and placebo.
- Unblinding will only occur when it is deemed medically necessary.

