#### 6.2.2 Study Visit 1- Baseline Testing and Initiation of the Intervention

Study Visit 1 (Baseline measurements) will occur 0-30 days after the Screening Visit. The following procedures will be performed during this visit:

- Medical history
- Concomitant medication review
- Health assessment
- Clinical blood specimen
  - Blood chemistry
    - o Lipid
    - HbA1C
  - CPK
  - Research blood specimen
- Liver stiffness
- Liver fat fraction
- Baseline risk factor questionnaire

- Baseline symptom assessment
- Study agent
  - Dispense the study agent (one bottle of 120 capsules) and review instructions for how to take it
  - Dispense and review the study diary

## 6.2.3 Study Visit 2

Study Visit 2 will occur 1 month (± 15 days) after initiation of the Intervention. The following procedures will be performed during this visit:

- Symptom/adverse events assessment
- Medical history
- Concomitant medications review
- Health assessment
- Clinical blood specimen
  - Blood chemistry
  - o Lipid
- Imaging review
- Study agent
  - Collect study agent and diary
  - Assess compliance (pill count)
  - Review study diary
  - Dispense study agent (same bottle that was brought to the visit/collected for pill count)

## 6.2.4 Study Visit 3

Study Visit 3 will occur 3 months ( $\pm$  15 days) after initiation of the intervention (study drug initiation).

The following procedures will be performed during this visit:

- Symptom/adverse events assessment
- Medical history
- Concomitant medications review
- Health assessment
- Imaging review
- Study agent
  - Collect study agent and diary
  - Assess compliance (pill count)
  - Review study diary
  - o Dispense study agent (one new bottle of 120 capsules) and diary

## 6.2.5 Study Visit 4

Study Visit 4 will occur 6 months ( $\pm$  15 days) after initiation of the Intervention (study drug initiation). The following procedures will be performed during this visit:

- Symptom/adverse events assessment
- Medical history
- Concomitant medications review
- Physical assessment
- Clinical blood specimen
  - Blood chemistry
  - o Hba1c
  - $\circ$  AFP
- Research blood specimen
- Follow-up risk factor questionnaire

- Imaging review
- Study agent
  - Collect study agent and diary
  - Assess compliance (pill count)
  - Review study diary
  - Dispense study agent (one bottle of 120 capsules) and diary

## 6.2.6 Study Visit 5

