## 6.5 Clinical Laboratory Minimum Test Requirements

Blood Chemistry	Lipid Panel	Other Blood Tests
Alanine aminotransferase	Total cholesterol	Hemoglobin A1C (HbA1C)
(ALT (SGPT))	High density lipoprotein (HDL)	Creatine phosphokinase
Aspartate aminotransferase	cholesterol	(CPK)
(AST (SGOT))	Low density lipoprotein (LDL)	Prothrombin Time (PT/INR)
Alkaline phosphatase (ALP)	cholesterol	Alpha-fetoprotein (AFP)
Bilirubin, total	Triglycerides	
Creatinine		
Glucose		
Sodium		

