## 8.0 SPECIMEN MANAGEMENT

- Clinical lab testing for blood chemistry, prothrombin time, a lipid panel, hemoglobin A1C, creatine phosphokinase, and AFP will be conducted or coordinated by the clinical laboratories at each institution.
- Research blood specimens and transplant tissue specimens will be collected, processed, and tested as described in the *Laboratory Manual*.

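### Post-baseline lipid results, chiefly the month 1 panel, are not masked from site staff who must stay blinded, so the arm can be guessed better than chance

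*Combined protocol and SAP*

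**What the plan says.** **The drug and the test.** Section 1.2 says that pravastatin "is a lipid-lowering agent". Section 3.1.2, under the clinical blood specimen, states: "Clinical labs include blood chemistry, lipid panel, hemoglobin A1C, creatine phosphokinase (CPK), and prothrombin time". It gives two purposes for these bloods: baseline values and watching for adverse effects. It also says that tests already in the record from the past 30 days are not repeated. Section 6.5 defines the lipid panel as total cholesterol, HDL, LDL and triglycerides.

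**When and where.** Sections 6.2.2, 6.2.3 and 6.2.7 and the schedule table in 6.4 place the panel at Visit 1 (month 0), Visit 2 (month 1) and Visit 6 (month 12). Section 8.0 says that "a lipid panel, hemoglobin A1C, creatine phosphokinase, and AFP will be conducted or coordinated by the clinical laboratories at each institution".

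**Who sees results.** The schema lists for Visit 2: "Review medical history, medications, and laboratory test results; symptom assessment; ECOG performance status; blood draw". Section 3.1.1 has a study physician or research coordinator take relevant laboratory results from the patient or the chart.

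**Who must be blinded.** Section 5.3 requires that "the identity of test and control treatments will not be known to investigators, research staff, or subjects". It names only the Cedars-Sinai study biostatisticians and the site investigational pharmacists as unblinded, and 10.3.2 agrees. Section 5.3 covers randomization blocks, pharmacy handling and unblinding requests. It does not mention laboratory results.

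**The concern.** Over-encapsulation protects the blind by appearance. It does not protect a blood value that the drug is meant to move. Section 4.2 excludes statin use in the previous 12 months and current use of gemfibrozil, niacin or fibrates. The Visit 1 panel is therefore off statin, and some other explanations for a later fall are removed. A physician or coordinator who sets the month 1 panel beside it has information about the arm that 5.3 says they should not have.

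Several judgements stay with people who can see the result or could learn of it:

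- Grade, attribution and expectedness of adverse events are decided by a study physician (3.1.1). Attribution feeds the holds and discontinuations in 5.4.
- Withdrawal can follow the investigator's or treating physician's judgement (6.7).
- Under 2.3, a death from HCC is a TTR event and any other death is censored. No blinded adjudicator is named.

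The planned analytic sample is 47 per arm, so a handful of judgements that differ by arm would matter.

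**Working it through.** There is no figure in the plan to reproduce. The check has three parts.

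**1. Does the chain hold?** A lipid-lowering drug (1.2), a pre-dose panel and an on-treatment panel (6.2.2, 6.2.3, 6.4), local laboratories (8.0), and review of laboratory results by staff who must be blinded (schema, 3.1.1, 5.3). No visible text breaks the chain. The month 1 result arrives with 12 − 1 = 11 months of treatment left. The month 12 result arrives when treatment and the 12-month TTR window end. It can then touch mainly the adverse event assessment at Visit 6 and in the follow-up calls of 6.3.

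**2. Who has a month 1 panel?** The 30-day rule in 3.1.2, read literally, can skip it. A panel drawn on day 0 is still current up to day 30. The schema gives Visit 2 as day 30 ± 5 (days 25 to 35), while 4.5 and 6.2.3 give ± 15 days (about days 15 to 45). The days on which the Visit 1 panel would still count are:

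- ± 5 window: days 25 to 30, which is 6 of 11 days.
- ± 15 window: days 15 to 30, which is 16 of 31 days.

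The documents do not say how visits will spread over those days, so the share of patients without a month 1 panel is unknown. For such a patient the next scheduled panel is Visit 6.

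**3. How well could the arm be guessed?** The size of the LDL effect and its spread are assumptions, because the documents give neither. Assume 1:1 allocation, normally distributed percent change with the same SD *s* in both arms, a mean difference *d*, and a cut-off midway between the arm means. Then

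P(correct) = Φ(d / (2s)).

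For example, d = 20 and s = 15 gives Φ(0.667) = 0.748. The full grid is:

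| d (extra LDL fall, %) | s = 10 | s = 15 | s = 20 | s = 25 |
|---|---|---|---|---|
| 10 | 0.691 | 0.631 | 0.599 | 0.579 |
| 15 | 0.773 | 0.691 | 0.646 | 0.618 |
| 20 | 0.841 | 0.748 | 0.691 | 0.655 |
| 25 | 0.894 | 0.798 | 0.734 | 0.691 |
| 30 | 0.933 | 0.841 | 0.773 | 0.726 |

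The range is 58% to 93%, against 50% with an intact blind. Every cell is above chance and none is near certainty for each patient.

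**4. Is the result used?** Lipids are not an endpoint (2.3), not an eligibility criterion (4.1, 4.2), and not part of a hold, discontinuation or accrual-stop rule (5.4, 5.7).

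**The case against.** The case on the other side is substantial, and much of it limits the point.

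- **The panel has a stated purpose.** One might infer from part 4 of the working that the post-baseline panel is useless. Section 3.1.2 does not support that, since it lists lipids among bloods drawn to monitor adverse effects. This stands, and it argues for masking the result over deleting the test.
- **Some patients may have no month 1 panel.** The 30-day rule makes this possible, so it cannot be said that the arm is open to inference in most patients.
- **The accuracy figures are assumed.** The midpoint cut-off also credits staff with knowing both distributions. The figures illustrate the leak and do not estimate it.
- **The imaging endpoint is protected.** Under 3.1.3, recurrence is read by independent reviewers outside the care team, and the schema sets surveillance scans at months 3, 6, 9 and 12. Bias in scan interpretation is not supported.
- **Dosing after recurrence cannot alter TTR.** Section 6.7 allows investigator discretion there, but TTR has already ended at first recurrence.
- **The accrual stop in 5.7 needs a lot to move it.** It requires 30% of participants off agent for serious events judged probably or definitely related. Nothing shows that partial knowledge of the arm would shift it.
- **The protocol does not say who attributes death.** This route is open but not proven to run through site staff. Naming an adjudicator is a separate matter that masking lipids would not settle.
- **Masking may exist elsewhere.** The Laboratory Manual, Pharmacy Manual and MOP are not among the documents, and the review text does not single out lipids.

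None of this supplies a masking step in the protocol itself, and the month 1 comparison remains available wherever the panel is drawn.

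**Conclusion.** The point stands as a gap in the blinding plan that is cheap to close. Post-baseline lipid results, chiefly at month 1 and to a lesser degree at month 12, can reach staff who must be blinded, and the protocol contains no step to stop it. Where the month 1 panel is drawn, the arm can be guessed better than chance: about 58 to 93% correct under an assumed extra LDL fall of 10 to 30% and an SD of 10 to 25 points. What is exposed is adverse event grading and attribution, withdrawal decisions and attribution of death.

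A reader might go further and infer that the panel discloses each patient's arm, or that the trial could not be reported as double-blind. The documents do not support either. They give no effect size, no assumed scenario yields certainty, some month 1 panels may be skipped, and recurrence on imaging is read centrally.

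**What to change.** Add to 5.3, with matching text in 3.1.2 and 8.0, that lipid results after Visit 1 are withheld from investigators, coordinators and participants until database lock. Until then, do one of the following:

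- Route the results to a person outside the site team who is already unblinded or takes no part in assessments. This keeps the monitoring purpose stated in 3.1.2.
- Assay lipids in batch from the research blood already drawn at Visits 1, 4 and 6, if the stored specimens prove suitable. The documents do not say whether they are. This route would not give a month 1 value.

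Keep the pre-dose Visit 1 panel visible. If the Laboratory or Pharmacy Manual already masks these results, one sentence in 5.3 saying so is enough. State as well how the 30-day rule applies to the Visit 2 panel, and reconcile the two Visit 2 windows.

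The cost is protocol wording and a reporting route at each laboratory. Endpoints and sample size do not change. The downside is that sites lose sight of a protocol-driven lipid value, and lipids ordered for routine care may still be seen.

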## 5.0 TREATMENT PLAN

## 5.1 Treatment Dosage and Administration

One hundred and thirty participants with liver cirrhosis and an initial HCC diagnosis will be randomized into one of 2 groups: 65 participants will be randomized to receive 40 mg pravastatin per day and 65 participants will be randomized to receive a placebo identical in color, consistency, and appearance to pravastatin 40 mg. Pravastatin and placebo will be provided as over-encapsulated tablets. Dosing will extend for 12 months

- Agent(s): Pravastatin and placebo
- Daily dose(s) and regimen(s) for each agent: One capsule per day
- Duration for each agent: Daily treatment for 12 months

The usual recommended dose of pravastatin is 10-40 mg/day, and the toxicity and tolerability are comparable for 20 mg and 40 mg (21-23). In a prior published trial of patients with chronic hepatitis or cirrhosis and HCC, pravastatin dosing began at 20 mg and was titrated up to 40 mg, and no serious side effects or discontinuation of therapy were noted (37). Thus, we feel that a 40 mg dose will be well-tolerated by the participants in this trial.

Patients will self-administer the 40 mg capsule of pravastatin or placebo daily in the evening. Patients will be instructed to take the study agent at bedtime or with an evening meal. Each participant will be given one bottle of 120 capsules at Study Visit 1 (90-day supply + buffer) and one bottle of 120 capsules (90-day supply + buffer) at Study Visit 3 (Month 3), Study Visit 4 (Month 6), and Study Visit 5 (Month 9).

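### The 30-day look-back for clinical labs in section 3.1.2 has no on-treatment condition, so read literally a pre-dose chemistry can replace the month-1 ALT/AST test at Visit 2

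*Combined protocol and SAP*

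**What the plan says.** All references are to the combined protocol and SAP.

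- **The rule.** Section 3.1.2 gives the clinical blood specimen two purposes: to set baseline levels and to "monitor for potential adverse effects of the intervention". One look-back serves both: if a patient's lab "results are current (within the past 30 days) in the medical record, labs will not be retested". No visit is named, and nothing is said about whether the sample must follow the first dose.
- **The neighbouring rule.** The eligibility specimen, described just above it, has a similar look-back, but that one is confined to results within eligibility range and ends "labs will not be re-tested at the Screening visit".
- **Where the rule reaches.** Section 6.2 sends the reader to 3.1 for definitions. Section 6.2.3 lists a clinical blood specimen, with chemistry and lipids, at Visit 2. Section 6.5 places ALT and AST in the chemistry panel.
- **Dosing.** Section 5.1: "Each participant will be given one bottle of 120 capsules at Study Visit 1", and "Patients will self-administer the 40 mg capsule of pravastatin or placebo daily in the evening".
- **Visit 2 timing.** Section 6.2.3: "Study Visit 2 will occur 1 month (± 15 days) after initiation of the Intervention" (section 4.5 agrees). The study schema is tighter: "Study Visit 2 (30 days ± 5 days after initiation of intervention".
- **The commitment.** Section 1.2 undertakes to test liver function at 30 days, again at 60 days, and then every 3 months. It calls that frequency adequate and says therapy stops when AST or ALT is above 5x ULN. Section 5.4 discontinues permanently at the same threshold when the event is at least possibly related.
- **The schedule.** Section 6.2 and the schedule of events list chemistry at Screening and at Visits 1, 2, 4 and 6. After Visit 2, the next one is at Visit 4 ("Study Visit 4 will occur 6 months", ±15 days, after initiation).

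**The concern.** Visit 2 carries the first listed on-treatment ALT/AST check. Its purpose is to show whether transaminases have risen on study drug, and the stopping rules above 5x ULN depend on such checks. A sample drawn before the first dose cannot show that. Yet the look-back would let such a sample fill the Visit 2 slot, and a coordinator following 3.1.2 exactly would have grounds not to draw.

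Two features of the protocol make the check worth protecting. Entry allows AST and ALT up to 5x ULN (4.1.6) in Child-Pugh A or B cirrhosis, so a patient can start close to the stopping threshold. And section 1.2 uses the monitoring frequency as part of its case for giving a statin to patients whose liver disease is a contraindication on the label.

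**Working it through.** The plan gives no figure to reproduce. The check is a day count.

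**Inputs.** Day 0 is Visit 1; months are taken as 30 days. The look-back is 30 days (3.1.2). The Visit 2 window is days 15-45, 31 days (6.2.3), or days 25-35, 11 days (schema). Visit 4 is days 165-195, and the earliest Visit 6 is day 345 (±15 days). Let g be the age in days, at Visit 1, of the chemistry that fills Visit 1: g = 0 if it is drawn that day, and larger if a Screening or standard-of-care result was used.

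**Step 1: is the Visit 1 sample pre-dose?** Drug is handed out at Visit 1 and taken in the evening (5.1), so a sample taken at the visit precedes the first dose.

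**Step 2: on which Visit 2 days does it still count?** It counts on day d when d + g ≤ 30.

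- ±15 window: max(0, 30 - 15 + 1 - g) = max(0, 16 - g) days.
- ±5 window: max(0, 30 - 25 + 1 - g) = max(0, 6 - g) days.

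| g (days) | ±15 window | ±5 window |
|---|---|---|
| 0 | 16 of 31 (days 15-30) | 6 of 11 (days 25-30) |
| 5 | 11 of 31 | 1 of 11 |
| 10 | 6 of 31 | 0 of 11 |
| 16 or more | 0 | 0 |

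From day 31 on, a day-0 sample is too old and a fresh draw is required unless another recent result exists. If the limit is read as excluding day 30 itself, the g = 0 counts become 15 of 31 and 5 of 11.

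**Step 3: are later visits affected?** The look-back starts at visit day minus 30.

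- Visit 2: 15 - 30 = day -15, up to 45 - 30 = day +15.
- Visit 4: no earlier than 165 - 30 = day 135.
- Visit 6: no earlier than 345 - 30 = day 315.

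Only Visit 2 can reach back before the first dose.

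**Step 4: how late is the first on-treatment ALT/AST if Visit 2 (days 15-30) is filled this way?**

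- Day-60 test in 1.2 is done: 60 - 30 = 30 to 60 - 15 = 45 days later.
- Only the section 6 chemistry is done, next at Visit 4: 165 - 30 = 135 to 195 - 15 = 180 days later.
- The schema also shows a blood draw at Visit 3 (days 75-105) without naming chemistry, and 6.2.4 lists none. If it did include chemistry: 75 - 30 = 45 to 105 - 15 = 90 days later.

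The spread between these cases comes from the disagreement between 1.2 and section 6 about tests after month 1. That is a separate matter. The part due to the look-back alone is the first line.

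**The case against.** The best defence is that nobody would read the rule this way. Section 6.2.3, the schedule table, the schema and section 1.2 all call for bloods at about month 1. On the literal reading, a Visit 1 draw would cancel the Visit 2 chemistry on its own target date, day 30. A sentence of convenience is more naturally read as sparing patients a duplicate of routine-care labs. That is probably the intent, and section 1.2 supports it. But the visit listings do not settle the matter, because 3.1.2 is where the protocol says when the listed specimen is actually drawn. Nor is the rule needed only for baseline, since 6.1 separately lets clinically indicated tests supply baseline values.

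A second objection is that the protocol never says the trial's own Visit 1 results count as chart results. This stands as a limit. Section 8.0 has clinical labs run or coordinated by each institution's clinical laboratory, which makes filing likely but is not a statement of it. Without that step, only a recent Screening or standard-of-care chemistry could qualify, on fewer days.

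Third, the safety weight is small. Section 7.1 recommends liver tests before treatment and afterwards only on clinical indication. The trial of pravastatin 80 mg cited in 1.2 found ALT doubling in 8% on drug and 13% on placebo. Monthly calls and the Visit 2 adverse event review continue. This also stands, with one qualification: neither the calls nor the review requires ALT/AST, and 7.1 notes that earlier transaminase rises came without clinical signs, so symptom review is a weak substitute.

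A reader might infer more than the documents support:

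- *That about half of participants would lose the month-1 test.* The 16 of 31 counts permitted calendar days; nothing gives the distribution of visits or of chart results. The target date also sits on the boundary: with a 31-day month it falls on day 31, when a day-0 sample no longer qualifies.
- *That the look-back leaves patients untested until month 6.* That follows only if the day-60 test in 1.2 is also not done.
- *That the protocol deliberately waives the test.* Section 1.2 shows the opposite intent.

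**Conclusion.** The point holds as a drafting gap. As written, 3.1.2 lets a pre-dose chemistry that is 30 days old or less stand in for the Visit 2 ALT/AST test, contrary to the 30-day test in 1.2. For a day-0 sample this covers Visit 2 on days 15-30 (±15 window) or days 25-30 (±5 window). Where it happens, the look-back itself delays the first on-treatment ALT/AST by 30-45 days; anything longer belongs to the separate conflict between 1.2 and section 6.

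This rests on three assumptions: that 3.1.2 is applied as worded, that the pre-dose result is in the medical record, and that a month is 30 days. The Manual of Procedures was not available and may already restrict the rule, so this is a statement about protocol wording and not about site practice. Frequency cannot be derived from the documents. The safety effect is modest, and power and the primary analysis are unaffected. It should be fixed because a stated rule, followed exactly, removes a stated safety check, and one clause cures it.

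**What to change.** Add to the clinical blood specimen paragraph in 3.1.2: *after Visit 1, a chart result may replace a clinical blood draw only if the sample was taken after the first dose of study agent and within the protocol window for that visit; otherwise the sample is drawn.* For Visit 2 the window is month 1 ± the stated margin. The clause should name which margin applies, since the schema (±5 days) and 6.2.3 (±15 days) differ.

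The window condition is needed. With the first-dose condition alone, a chart value from day 1 would still be current up to 1 + 30 = day 31 and could replace the month-1 test while saying little about a month of treatment. With both conditions, the Visit 2 days on which a pre-dose sample qualifies fall from 16 of 31 (or 6 of 11) to 0. Routine-care labs taken on treatment and in the window can still be used.

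The cost is one clause and a memo to sites, plus an occasional 10-15 mL draw at a visit that already lists it. The window condition also applies at Visits 4 and 6, so a few chart results that count today because they are under 30 days old would have to be repeated there.
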